Clinical evaluations including physical examinations, vital signs, laboratory tests, electrocardiograms and the assessment of adverse events will be performed for all subjects during hospitalization and at follow-up time points as measures of the safety profile.

Randomization: Randomization will be conducted prior to the diagnostic angiography.

Stratification: Randomized assignment of PZ-128 and placebo will be stratified for whether the cardiac catheterization ± PCI is being done on an elective or urgent basis at the time the operator decides to perform the procedure.

Sample Size/Power: The current design anticipates a sample size of 600 subjects who will undergo non-emergent cardiac catheterization ± PCI. The sponsor anticipates that the incidence of major plus minor bleeding among placebo-treated subjects will range from 2% to 6% on the basis of historical experience. Given the anticipated sample sizes and estimated range of incidences associated with placebo, the study will be able to demonstrate that the bleeding risk of PZ-128 is non-inferior to the risk associated with placebo with non-inferiority margins in the range of 2.6 to 7.6%, depending on the underlying bleeding risk of placebo. Given the anticipated benefits of PZ-128, these non-inferiority margins are reasonable for the planned safety decisions generated from this trial.

Statistical Methods: All subjects who are randomized will be considered evaluable for the analyses. The following statistical analysis will be provided for the primary endpoint. The point estimate of the difference in risk of any event of non-CABG TIMI major plus minor bleeding through 30 days post treatment for between PZ-128 and placebo (e.g., Pr (Event in PZ-128 patient)-Pr (Event in placebo patient)), and corresponding lower one-sided 95% confidence interval will be presented. These estimates will be generated using subjects who underwent diagnostic angiography for all PZ-128 treatment arms pooled across both doses (~400 subjects) and all placebo (~200 subjects) and descriptive results will also be generated for each individual dose. The proposed phase 2 study is not of sufficient size or of sufficient follow-up duration to allow formal analysis of clinical efficacy.

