7.5.4 Methodology

The primary objective of this study is to evaluate the safety of two dose levels of PZ-128 compared to placebo as measured by the incidence of TIMI major plus minor bleeding not related to CABG through 30 days after treatment. Specifically, the study will be designed to test the hypothesis that from a safety perspective, PZ-128 is non-inferior to placebo, where non-inferiority is demonstrating that the difference in risk of bleeding incidence between the two treatments is less than a specified clinically important margin; the acceptable safety margin will depend in part on the efficacy benefit found for PZ-128. Specifically, the analysis of the bleeding outcome variables will assess the risks of bleeding on the two treatment regimens by generating point and one-sided 95% confidence interval estimates of the risk difference using the following formula:

$$\text{Risk Difference} = \pi_{\text{PZ-128}} - \pi_{\text{Pbo}}$$

where $\pi_{\text{PZ-128}}$ is the bleeding incidence across the two PZ-128 arms and π_{Pbo} is the bleeding incidence for the placebo arm. The point and interval estimates for this risk difference will be obtained using a generalized linear model with the binomial distribution assumption and an identity link. To address the potential underlying risk differences associated subpopulations defined by underlying subject risk and whether or not the subject received CABG, those factors will be included in the model. The robust variance estimator as defined by Liang and Zeger [49] will be used to generate the interval estimates. Comparable models will be used to generate estimates for both the primary outcome and the secondary outcomes defined above.

Adverse Events

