7.6.1 Secondary Efficacy Endpoints

While the primary objective of this study is to determine the safety of PZ-128, secondary analyses will be used to evaluate potential efficacy signals that will allow an assessment of the comparative risk/benefit calculus of the treatment in determination of a future Phase 3 study.

Specific secondary efficacy outcome measures include:

- incidence of the composite endpoint of major adverse cardiac events (MACE)- any of cardiovascular death, non-fatal myocardial infarction, non-fatal stroke, recurrent ischemia requiring hospitalization or urgent coronary revascularization with either CABG or subsequent PCI evaluated through 30 days and 90 days after treatment;

- incidence of the individual components of the MACE composite as measures of potential clinical benefit evaluated through 30 days and 90 days after treatment:
 - cardiovascular death
 - non-fatal MI
 - non-fatal stroke
 - recurrent ischemia requiring hospitalization
 - urgent coronary revascularization
- incidence of definite or probable stent thrombosis evaluated through 30 days and 90 days after treatment;
- effect of the investigator choice of P2Y₁₂ inhibitor (i.e., clopidogrel versus prasugrel/ticagrelor) on the individual components of the MACE composite measure through 30 days and 90 days post treatment.

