7.6.2 Methodology

The proposed phase 2 study is not of sufficient size or of sufficient follow-up duration to allow analysis of clinical event rates.

Two alternative approaches will be used to evaluate the differences in risk of the various secondary outcome measures. The first will utilize generalized linear models analogous to those used for the safety outcomes. In addition because each of these outcome measures can be evaluated using a time to event approach, survival analyses will be used to examine those outcomes. Kaplan-Meier estimates of the cumulative risk of each outcome will be calculated to investigate differences between the treatment groups in the time to occurrence, and a Cox Proportional hazard model that accounts for the risk stratification variables described above will be used to assess risk differences in the 3 treatment groups. All of these analyses will be interpreted descriptively, with no adjustment for multiple comparisons. We anticipate that some analyses will be conducted for specific subgroups (e.g., influence of baseline risk factors, concomitant therapies), but these subgroup analyses will again be considered exploratory and treated as descriptive analyses. Details will be provided in the SAP. Generalized linear models comparable to those used for the safety outcomes will also be used to evaluate the effect of investigator choice of P2Y₁₂ inhibitor on each of the MACE components.

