7.7 Determination of Sample Size/Power

Power calculations were used to evaluate the size of non-inferiority margins that were able to be detected from a study of 600 participants, 400 of whom are randomized to PZ-128 and 200 of whom are randomized to placebo. Available data on bleeding rates from previous studies [29, 32, 33] suggest that the incidence of bleeding in the placebo arm is likely to be in the range of 2% to 6%. Furthermore, the sponsor assumes that the true difference in the incidence

of the participants on the PZ-128 arms and those in the placebo arms are likely to be in the range of 0% to 2%. Based on these assumptions, the table below shows the minimum non-inferiority margin that could be demonstrated with at least 80% power, where that non-inferiority margin is based on the upper limit of the 95% confidence interval identified above. This sample size is adequate to demonstrate acceptable upper safety bounds.

True Incidence or Risk of Bleeding for placebo	Minimum Demonstrable Non-inferiority margin	
	True Incidence Difference of 0%	True Incidence Difference of 2%
2%	2.6%	5.0%
3%	3.2%	5.5%
4%	3.7%	5.9 %
5%	4.1%	6.3%
6%	4.4%	6.6%

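### The robust-variance risk-difference intervals extend to secondary outcomes that may be sparse, with no rule for arms that have zero or few events

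*Combined protocol and SAP*

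**What the plan says.** Section 7.5.4 estimates the bleeding risk difference with a "generalized linear model with the binomial distribution assumption and an identity link". On precision it says: "The robust variance estimator as defined by Liang and Zeger [49] will be used to generate the interval estimates". The section describes "generating point and one-sided 95% confidence interval estimates of the risk difference". Underlying subject risk and CABG status enter as covariates.

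The scope is then widened: "Comparable models will be used to generate estimates for both the primary outcome and the secondary outcomes defined above". Section 7.5.2 lists those outcomes as minimal bleeding, clinically significant bleeding and CABG-related bleeding. For efficacy, Section 7.6.2 names two approaches. On the first it says: "The first will utilize generalized linear models analogous to those used for the safety outcomes". The second is Kaplan-Meier and Cox. The outcomes in Section 7.6.1 include MACE, its five components taken singly (among them cardiovascular death and non-fatal stroke), and "incidence of definite or probable stent thrombosis evaluated through 30 days and 90 days after treatment".

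The documents contain no exact, score or small-sample method, and no statement of what is reported when an arm has no events. Section 7.2 leaves data-handling conventions to the SAP.

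**The concern.** For independent binary data with treatment as the only term, the sandwich variance of an identity-link risk difference is the unpooled Wald variance. An arm with no events contributes nothing to it. The interval is therefore too short when one arm is empty, and has zero width when both are.

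The outcomes most exposed are serious ones: cardiovascular death, stroke, stent thrombosis and CABG-related bleeding. Section 7.6.1 says the efficacy analyses inform the risk/benefit judgement for Phase 3, and Section 7.5.4 makes the acceptable bleeding margin depend partly on the efficacy found. An interval of 0 to 0 would show certainty where the data exclude little. A short interval on the other side of zero could suggest harm that is not there.

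**Working it through.** **Inputs.** 400 PZ-128 and 200 placebo subjects (Section 7.7), and one-sided 95% limits with z = 1.645 (Section 7.5.4). The documents give no incidence for the sparse outcomes, so 0.1% to 1% is an assumption. All pairs below are PZ-128 first, placebo second.

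**The plan's own figures.** Nothing in the plan states precision for sparse outcomes. The only related figures are the margins in Section 7.7, used in step 4 only as points at which to evaluate error. They do not reproduce at one-sided 5% and 80% power: for placebo 2% and no true difference, (1.645 + 0.842) × sqrt(0.02×0.98/400 + 0.02×0.98/200) = 3.01%, against 2.6% in the table. That is a separate matter.

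**1. Intervals for given counts.** Specified limits: d ± 1.645 × sqrt(p1(1−p1)/400 + p0(1−p0)/200). Comparator: Miettinen-Nurminen score limits.

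| Events | Specified limits (points) | Score limits (points) |
|---|---|---|
| 0 vs 0 | 0.00, 0.00 | −1.34, +0.67 |
| 4 vs 0 | +0.18, +1.82 | −0.34, +2.21 |

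For 4 vs 0: d = 1.00 and SE = sqrt(0.01×0.99/400) = 0.4975 points, so the limits are 1.00 ± 0.82. The lower limit excludes zero. Yet under 2:1 allocation and no true difference, four events all fall in the PZ-128 arm with probability about (2/3)^4 = 20%.

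**2. How often arms are empty**, with equal assumed incidence p. No events in either arm: (1−p)^600. At least one empty arm: 1 − [1−(1−p)^400][1−(1−p)^200].

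| p | Neither arm has events | At least one arm empty |
|---|---|---|
| 0.1% | 55% | 94% |
| 0.2% | 30% | 82% |
| 0.5% | 5% | 45% |
| 1% | 0.2% | 15% |

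**3. Miss rates of nominal 5% limits**, by exact enumeration of the two binomials.

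- Upper limit, 0.4% vs 0.2%: 14.7% (score 6.9%). Most of this is the 0-to-0 interval, with probability 0.996^400 × 0.998^200 = 13.5%.
- Lower limit, 0.25% vs 0.5%: 36.7% (score 0.1%). With no placebo events the specified lower limit never falls below about −0.16 points (the 1 vs 0 case: 0.25 − 1.645×0.25). It therefore misses the true −0.25 whenever placebo has no events, which has probability 0.995^200 = 36.7%.
- Upper limit at equal rates of 0.1%, 0.2%, 0.5% and 1%: 0.1%, 0.4%, 1.7% and 2.8%. Here it over-covers.

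**4. Primary endpoint.** At placebo 2% to 6% the expected placebo count is 4 to 12, so this is a different regime. At the ten tabulated margins the exact error of the specified upper limit is 4.3% to 4.8%.

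**5. Covariates.** Steps 1 to 4 use the unadjusted model. With covariates and empty cells the fit may fail instead. CABG-related bleeding cannot occur without CABG, yet CABG status is in the model. One covariate level therefore has zero risk, on the boundary of the identity link. This follows from the endpoint definition and needs no assumed rate.

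**The case against.** The case for leaving the plan alone has weight. Section 7.6.2 reads the efficacy analyses descriptively, says the study is not sized for clinical event rates, and adds Kaplan-Meier and Cox. Deaths and SAEs are listed individually (Section 7.5.4), so a reader would see 0/400 and 0/200. Failure of an adjusted model to fit is visible to the analyst. Details are left to the SAP.

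These points limit the consequence but do not remove the defect. The protocol does not leave the variance method open; it names one that gives wrong error bars for empty arms. Descriptive intervals still have to be honest, and these feed the risk/benefit judgement. Cox does not help when an arm has no events, because the hazard ratio cannot then be estimated.

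The score interval is also imperfect. Its upper limit misses 6.9% of the time at 1% in both arms, 10.5% at 0.25% vs 0.5%, and about 13% at 0.1% vs 0.4%; in the last two cases the specified upper limit misses under 1%. This stands, and it argues against replacing every interval in the trial.

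**Conclusion.** The point holds for secondary outcomes with zero or few events in an arm, because the plan prescribes an interval that collapses there and gives no alternative. The intervals in step 1 depend only on the counts and the unadjusted model. The frequencies in steps 2 and 3 depend on assumed incidences.

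Three stronger readings are not supported:

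- A reader might infer that the primary non-inferiority bound is also too short. It is not: its error is slightly below the nominal 5%, the cautious direction for a safety claim. This concerns the upper limit. The Synopsis says a "corresponding lower one-sided 95% confidence interval will be presented", while Section 7.7 says the "margin is based on the upper limit of the 95% confidence interval identified above". That wording should be reconciled, since non-inferiority on bleeding needs the upper limit.
- A reader might infer that all secondary outcomes will be sparse. Clinically significant bleeding includes TIMI major and minor events, and minimal bleeding has no stated reason to be rare.
- A reader might infer that the specified interval is always too short for rare outcomes. At equal low rates its upper limit over-covers. The failure depends on direction and on the true difference.

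**What to change.** In the SAP, keep the planned model and interval for the primary outcome and for secondary outcomes that are not sparse. For any secondary outcome with few events in either arm, under a threshold set before unmasking (for example fewer than 5), report the event counts with a Miettinen-Nurminen score or exact interval for the unadjusted or stratified risk difference. Apply the same fallback to any outcome where the model does not converge. The count threshold should exempt the primary explicitly: at a placebo incidence of 2% only 200 × 0.02 = 4 placebo events are expected, so the example threshold could otherwise change the primary method without need.

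The cost is SAP wording and standard software. Intervals for rare outcomes become wider and lose covariate adjustment, and score limits remain approximate (step 3 and the objection above give their miss rates).

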The phase 2 subject population will consist of approximately 600 low-to-moderate risk subjects including those undergoing elective PCI and subjects with NSTEMI-ACS. Outcomes will be assessed over 30 day and 90 day time periods. Higher risk subjects with STEMI or those requiring GPI therapy will be excluded. Based on the phase 1 data with PZ-128 which documented anaphylactoid/histaminic reactions in some subjects at high doses of 1-2 mg/kg, subjects with baseline hypotension (systolic blood pressure <95 mm Hg) or history/high risk of drug allergies will be excluded, and a prophylactic anti-histamine regimen will be incorporated. Based on the extensive clinical data with vorapaxar, subjects with a prior history of stroke or transient ischemic attack, or body weight of <60 kg will also be excluded. Bleeding is the most common and severe side effect of anti-thrombotic and/or anti-platelet agents in general. In standard-of-care treatment, subjects undergoing PCI may be exposed to several of these medications (e.g., ASA, P2Y₁₂ inhibitor, heparin). When introducing additional potent anti-platelet agents in this setting such as PZ-128, potential efficacy must be balanced against a possible increase in the frequency of bleeding events. The design of the primary outcome measure in this study (relative bleeding rate of PZ-128 vs placebo) is consistent with established practice for evaluation of bleeding events in subjects undergoing cardiac catheterization with intent to perform PCI in phase 2 studies such as TRA-PCI. Addition of an antiplatelet agent to existing standard-of-care in this setting, so-called dual anti-platelet therapy (DAPT), has been studied extensively and found to be beneficial [7]. As PZ-128 is an effective platelet aggregation inhibitor with a unique intracellular mechanism, consequently assessing bleeding (hemostasis) will be the primary endpoint in the present study from a safety and feasibility perspective. Although not sufficiently powered, an early efficacy signal (e.g. reduction in MACE or stent thrombosis) may be detected in this 600 subject study as occurred in earlier studies with oral PAR1 inhibitors (vorapaxar, atopaxar). Thus, this design offers the opportunity to assess the safety and potentially early efficacy of PZ-128 in a setting of current clinical practice.

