A medical history will be obtained by the investigator or qualified designee. Subject history should include information on family history and personal history. Subject history should include information concerning family history of chest pain and/or heart attack, general cardiac history, alcohol intake, smoking, as well as other coronary risk factors such as diabetes, hypertension, dyslipidemia, and obesity. Particular attention and documentation should be given to the subject's cardiac history, the clinical evaluation leading to the cardiac catheterization procedure (i.e., CAD presentation, Canadian Cardiovascular Society Classification for angina, Thrombolysis in Myocardial Infarction Risk Score for UA/NSTEMI, and New York Heart Association Classification of Functional Status for heart failure), bleeding history and allergy history (drugs, IV contrast media, food, stings and atopic conditions and any required treatment/ medical intervention).

- **Physical Examination: Screening, 24-hour/Discharge*, 14-day Visit**

The investigator or qualified designee will perform an examination to include skin, head, neck, pulses, lungs, heart, abdomen, extremities, and gross neurologic system. Abnormal findings not present at screening or abnormal findings that were present at screening but have become worse in severity/grading over baseline will be considered adverse events and recorded as per the AE procedures in **Section 6.7.2.2**.

*Note, the clinical site's standard of care, cardiac catheterization nursing assessment may be performed to evaluate the subject's clinical status in lieu of a complete physical exam at the 24 hour/discharge time point. This exam should be completed by qualified nursing staff with particular attention being paid to signs/symptoms related to the known side effects of PZ-128 (i.e., allergic reaction, injection site reaction and paresthesia) and other possible side effects from the procedure and/or concomitant medications (i.e., bleeding).

- **Vital Signs Assessment: Screening, Just Before Study Drug Infusion, Just After Completion of Study Drug, After Catheterization/PCI, 24-hour/Discharge, 14-day Visit**

At screening, the investigator or qualified designee will measure blood pressure and

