Severe symptoms, such as clinically significant hypertension or hypotension, dyspnea, bronchospasm, angioedema or generalized urticaria require immediate discontinuation of the study drug and aggressive symptom management. The criteria for the diagnosis of Anaphylaxis [48] is attached in **Appendix C**. Anaphylaxis is a medical emergency that requires prompt recognition and immediate discontinuation of the study drug and intervention/treatment. A subject who experiences anaphylaxis will not be re-challenged with the study drug.

Prompt and accurate documentation of any allergic reaction should include the following:

- Initial symptoms and course of progression
- The timing of symptom onset
- Intervention, timing and subject response
- Time of symptom resolution
- Discharge instructions (e.g., follow-up plans, prescribed medications, appropriate allergy referral, etc.) or transfer to emergency services.

The disposition and follow-up of subjects with an allergic reaction depends on the severity of the initial reaction, the response to treatment and the clinical judgment of the investigator and medical staff. Subjects with non-life-threatening symptoms should be observed for 4-6 hours after successful treatment (resolution of symptoms) if discharge is being considered. Subjects who have severe reactions/anaphylaxis with cardiovascular and/or respiratory symptoms or refractory symptoms should be admitted or treated and observed for a longer prior of time especially if the condition is not promptly resolved by therapy. Other high-risk groups include those on beta-blocker therapy who have significant reactions and those with severe late-phase or prolonged reaction. Some subjects who have problematic social situations (e.g., no phone) or live far from medical care may also require admission or prolonged observation.

Subjects experiencing any allergic reaction should be provided with education regarding risk with future exposure to agents that might initiate an allergic response and precautions at the time of discharge including instructions for seeking emergency medical care upon recurrence

of signs/symptoms.

Need for Administration of Prohibited Medications

There are no anticipated prohibitive medications in the case of a medical emergency.

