National Cancer Institute Common Terminology Criteria for Adverse Events (NCI CTCAE) version 4.0 will be used for AE/SAE reporting in the trial database. This version of CTCAE is MedDRA v12.0 (Medical Dictionary for Regulatory Activities Terminology) compatible at the AE (Adverse Event) term level where each CTCAE term is a MedDRA LLT (Lowest Level Term). All adverse events will be captured from the time of randomization up until 30 days after study drug administration and all serious adverse events will be captured from the time of randomization up until 90 days after study drug administration. AEs will be summarized by system organ class and preferred term using MedDRA, with summaries reported separately for the 3 treatment arms aggregated across all participants in those treatment arms, and stratified by the four risk groups defined by the cross-classification of whether subjects received CABG or not and the urgency of the procedure at the time the operator decides to perform the cardiac catheterization (i.e., elective versus urgent). All adverse event data will be listed for all subjects. Separate listings of all SAEs, deaths and discontinuations due to AEs will be presented. Adverse event data will be summarized by relationship and severity. All AEs relating to bleeding will be summarized separately.

Laboratory data

All laboratory data will be listed and absolute values outside the normal range will be flagged if applicable. Changes from pre-dose baseline at Screening may also be summarized. Numerical laboratory data will be summarized using standard summary statistics and will be presented by treatment group.

Other safety data

Physical examination, ECG, and vital signs data will be listed and summarized using standard summary statistics by treatment group.

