- a. Respiratory compromise (e.g., dyspnea, wheeze-bronchospasm, stridor, reduced PEF, hypoxemia)
 - b. Reduced BP or associated symptoms of end-organ dysfunction (e.g., hypotonia [collapse], syncope, incontinence)
2. Two or more of the following that occur rapidly after exposure to a *likely* stimuli for that subject (minutes to several hours):
 - a. Involvement of the skin-mucosal tissue (e.g., generalized hives, itch-flush, swollen lips-tongue-uvula)
 - b. Respiratory compromise (e.g., dyspnea, wheeze-bronchospasm, stridor, reduced PEF, hypoxemia)
 - c. Reduced BP or associated symptoms (e.g., hypotonia [collapse], syncope, incontinence)
 - d. Persistent gastrointestinal symptoms (e.g., crampy abdominal pain, vomiting)
 3. Reduced BP after exposure to *known* stimuli for that subject (minutes to several hours):
 - a. Infants and children: low systolic BP (age specific) or greater than 30% decrease in systolic BP
 - b. Adults: systolic BP of less than 90 mm Hg or greater than 30% decrease from that person's baseline

PEF, Peak expiratory flow; *BP*, blood pressure.

Modified from Sampson et al., 2006

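### Section 7.5.4 plans no grouped, by-dose summary of allergic/infusion reactions, a named side effect of PZ-128, although bleeding has one

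*Combined protocol and SAP*

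**What the plan says.** **The harm.** Section 4.2.1 reports that phase 1 "documented anaphylactoid/histaminic reactions in some subjects at high doses of 1-2 mg/kg". In response, subjects with low baseline pressure or an allergy history are excluded and "a prophylactic anti-histamine regimen will be incorporated". Section 6.6.1 tells nursing staff to watch for "known side effects of PZ-128 (i.e., allergic reaction, injection site reaction and paresthesia" among other signs. Sections 6.4.7.7 and 6.7.2.3 require anaphylaxis precautions during the infusion and for at least 1 hour after it. Section 6.7.2.3 separates mild-to-moderate skin symptoms (pruritus, flushing, rash), for which the infusion may be interrupted and restarted, from "Severe symptoms, such as clinically significant hypertension or hypotension, dyspnea, bronchospasm, angioedema or generalized urticaria", which require immediate discontinuation.

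**The analysis.** The secondary and exploratory safety endpoints in Sections 7.5.2 and 7.5.3 are all bleeding endpoints. For adverse events, Section 7.5.4 says "AEs will be summarized by system organ class and preferred term using MedDRA", separately for the three arms and also by four risk groups. It adds summaries by relationship and severity, a listing of every event, and separate listings of SAEs, deaths and discontinuations due to adverse events. One group of events gets its own summary: "All AEs relating to bleeding will be summarized separately". For blood pressure, "vital signs data will be listed and summarized using standard summary statistics by treatment group".

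**The concern.** A drug-allergic reaction is a syndrome whose signs belong to different parts of MedDRA: skin, respiratory and vascular. If the signs are recorded separately, the system-organ-class and preferred-term tables show several small rows, and none of them gives the number of subjects who reacted. Listings do not supply that number either. Section 7.5.4 also names no output for infusion interruptions and no count of subjects with a large fall in blood pressure.

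Section 4.1.2.2 says the programme's results will decide whether to proceed to Phase 3 and with which dosing regimen. For that decision, the frequency of a known, possibly dose-related effect at 0.3 and 0.5 mg/kg is worth one number per arm with an interval. If terms are grouped only after unmasking, the choice of terms is open to the criticism that it followed the data.

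**Working it through.** The plan states no rate, power or margin for allergic reactions, so there is no figure to reproduce. The check has two parts.

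**1. Which reactions reach which output**

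| Reaction | Route in the plan | One by-dose count of reactors? |
|---|---|---|
| Anaphylaxis | Named SAE (6.7.2.2.5) and mandatory stop (6.3.3): SAE and discontinuation listings | Listed, not estimated |
| Severe symptoms | Immediate discontinuation (6.7.2.3): discontinuation listing | Listed, not estimated |
| Non-serious, diagnosed as allergic reaction | Recorded as a diagnosis or syndrome (6.7.2.2): one term, shown by arm | Yes, in effect |
| Non-serious, recorded as symptoms because no diagnosis was made | Separate preferred terms, by arm | No |
| Interrupted and restarted | Adverse-event rows only; no interruption table | No |
| Blood-pressure fall | Listed; standard summary statistics | No threshold count |

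The gap is in the last three rows.

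**2. What splitting costs, as an illustration**

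Inputs from the documents: about 600 subjects at 2:2:1:1 with the two placebo groups merged (Section 7.1). That gives 600 × 2/6 = 200 at 0.5 mg/kg and 600 × (1 + 1)/6 = 200 on placebo.

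Assumptions, none from the documents: reaction rates p1 (0.5 mg/kg) and p0 (placebo); each reactor has one term; reactions divide evenly over k terms, which are treated as independent. Section 7.5.4 plans no hypothesis test of adverse events, so a one-sided Fisher test at 5% serves only as a yardstick for whether the arms separate.

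Formulas:
- q(k) = Σx Σy Bin(x; 200, p1/k) · Bin(y; 200, p0/k) · 1[Fisher p ≤ 0.05], by exact enumeration. Grouped means k = 1.
- Chance that at least one of k terms separates: 1 − (1 − q(k))^k.

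Expected counts at 6% v 1%: grouped 200 × 0.06 = 12 against 200 × 0.01 = 2. Over five terms: 12/5 = 2.4 against 2/5 = 0.4 per row.

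| p1 v p0 | Grouped | One given term, k = 3 / 4 / 5 | At least one term, k = 3 / 4 / 5 |
|---|---|---|---|
| 6% v 1% | 0.83 | 0.23 / 0.12 / 0.07 | 0.54 / 0.40 / 0.29 |
| 10% v 2% | 0.96 | 0.46 / 0.31 / 0.21 | 0.84 / 0.77 / 0.69 |
| 3% v 1% | 0.26 | 0.03 / 0.01 / 0.005 | 0.08 / 0.04 / 0.03 |

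A two-sided test at 6% v 1% shows the same pattern: 0.74 grouped, 0.13 for one of three terms, 0.02 for one of five.

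The event definition matters as much as the grouping. Keeping a 5-point excess but raising background, grouped power falls from 0.83 (6% v 1%) to 0.54 (10% v 5%) and 0.39 (15% v 10%).

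**The case against.** The strongest reply is that the plan already shows these events.

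- Section 6.7.2.2 has investigators record the diagnosis or syndrome when it is known, so a recognised reaction is one term. This stands, and it limits the scatter to reactions nobody diagnosed.
- A reader might infer that a dose-related excess could go unreported. The documents do not support that: Section 7.5.4 shows 0.3 and 0.5 mg/kg as separate arms, lists every event, and summarises by relationship and severity.
- A reader might infer that the anaphylaxis SAE misses first exposures, because the Appendix C criterion based on pressure alone ("systolic BP of less than 90 mm Hg or greater than 30% decrease") requires a stimulus already known for that subject. That is too strong. Another Appendix C criterion needs only a likely stimulus, and Section 6.7.2.2.5 also admits CTCAE Grade 3 or higher.
- A reader might infer that blood pressure is reduced to group means. The text promises listings and standard summary statistics. It names no threshold count, but it does not say means only.
- The phase 1 reactions occurred at 1-2 mg/kg, above both trial doses. Section 6.7.2.2.9 expects the trial doses to be well tolerated, and prophylaxis is given. No document supports rates of 6-10%.
- The single-term figures overstate the loss. A reader sees all rows, and a subject with several symptoms would count in several of them. The at-least-one column is the fairer comparison, though it carries no allowance for multiplicity.
- Section 7.2 defers detail to a later SAP that is not in the supplied text, and the known-toxicities text is partly redacted. A grouped analysis elsewhere cannot be excluded.

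What survives is that the plan as supplied gives bleeding its own summary and this named side effect none.

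**Conclusion.** The point holds in a limited form. Section 7.5.4 contains no grouped allergic/infusion-reaction summary, no between-arm estimate for one, no table of interruptions and no count of large pressure falls. The consequence is dilution, mainly of non-serious reactions: they can be spread over preferred terms and are never estimated as one rate per dose. It is not concealment, and severe reactions are captured by the SAE and discontinuation listings.

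The size is unknown because the documents give no reaction rates. Under the assumed 6% v 1%, grouping raises the chance of separating the arms from between 0.29 and 0.54 (at least one of five to three terms) to 0.83. Under 3% v 1%, even the grouped count reaches only 0.26, and its value is then the interval. The conclusion rests on some reactions being recorded as symptoms and on the later SAP not already grouping them. The bleeding analysis is unaffected. This is an inexpensive improvement to safety reporting.

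**What to change.** In Section 7.5.4 or the SAP, before unmasking, add a descriptive allergic/infusion-reaction summary in the safety set.

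- **Event.** A subject with an adverse event recorded as allergic or infusion reaction or as anaphylaxis (Section 6.7.2.2.5), or with a symptom listed in Section 6.7.2.3 that starts between the start of the infusion and 1 hour after its end, the protocol's own precaution period.
- **Sensitivity only.** Any longer window, and dyspnea or a blood-pressure change on its own. Section 6.7.2.2.3 lists dyspnea and hypotension as expected from the disease and procedure, and the last calculation above shows what added background costs.
- **Report.** n (%) by arm, and the risk difference with exact 95% confidence interval for 0.3 and for 0.5 mg/kg, each versus merged placebo.
- **Two further tables by arm.** (a) Infusion interruptions and discontinuations for a reaction. (b) Subjects whose post-infusion systolic pressure is below 90 mm Hg or more than 30% below the pre-infusion value. The Appendix C limits serve here as tabulation cut-offs only. Pressure is scheduled just before and just after the infusion, so falls that recover in between may be missed.

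**Cost.** SAP wording and a few tables from adverse-event, infusion and vital-sign records already planned. Check that the database holds onset times: Section 6.7.2.2 asks for onset dates, and Section 6.7.2.3 asks for symptom timing only for allergic reactions. Some non-specific procedural or contrast events will enter all arms. The placebo comparison guards against bias from these, but some precision is lost. No dose, treatment or stopping rule changes.
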